8.1.3 Acute Respiratory Distress, Pneumonia, and Sepsis Syndrome Classification

Enrolled participants will be evaluated for ARDS, pneumonia, and sepsis utilizing detailed, investigator driven review and application of published and accepted clinical criteria for each syndrome. To evaluate for ARDS, pneumonia, and sepsis, investigators will evaluate data and the clinical record for each participant for Study Day -2 through Day 7 while the patient is hospitalized (the phenotyping observation window). Individual criteria for each syndrome will be collected and recorded separately allowing for patients to be classified as ARDS, Sepsis, and/or Pneumonia using multiple published criteria (e.g., for sepsis using both “sepsis-2” and “sepsis-3” criteria). These data will then be used to code variables in our dataset that classify patients according to syndrome definitions. Standard operating procedures will be provided to each site to ensure accuracy and consistency of syndrome adjudication.

ARDS will be identified based on the Berlin Definition with the additional modifications proposed in the New Global Definition of ARDS.^{3,4} Trained physician investigators will determine the presence of potential precipitating factors for ARDS (e.g., sepsis, aspiration, pancreatitis). Chest radiographs and chest computed tomography scans conducted for clinical purposes during the observation window will be reviewed by trained physician investigators for bilateral infiltrates consistent with ARDS. The type of chest imaging, time and date of imaging acquisition, and bilateral infiltrates present, absent, or equivocal will be recorded in case report forms. The presence or absence of pleural effusions will also be recorded. Arterial blood gas (ABG) values drawn for clinical purposes and corresponding fraction inspired oxygen percentage (FiO₂) will also be recorded in case report forms. If an ABG is unavailable on a given day,

SpO₂ and corresponding FiO₂ will be recorded to calculate the S/F ratio. Invasive and non-invasive oxygenation and ventilation parameters will also be extracted from the medical record. We will apply strict physiologic criteria in ARDS definitions to determine the presence or absence of ARDS daily, timing when ARDS criteria are met, and the severity of ARDS based the level of hypoxemia (P:F and S:F ratios).

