16.3.2 Aim 3 Study Objectives

Primary objectives (Aim 3):

1. Identify acute phenotypes of APS in mechanically ventilated patients using bulk RNA sequencing of mononuclear cells isolated from NBBAL and identify their association with short-term and long-term clinical outcomes.
2. Identify acute phenotypes of APS in mechanically ventilated patients using a panel of protein biomarkers measured in exhaled breath condensate obtained from HME filters on day 1 of mechanical ventilation along with clinical respiratory variables and identify their association with short-term and long-term clinical outcomes.

Secondary objectives (Aim 3):

1. Use longitudinal collection of HME filter fluid to determine whether phenotypes identified at the onset of acute respiratory failure are stable over time and whether new respiratory phenotypes emerge.
2. Determine which biologic processes in the airspaces are reflected in the bloodstream and which processes are lung-specific by comparing bulk RNA sequencing of mononuclear cells from blood and lungs and proteins measured in HME fluid and plasma.
3. Determine whether phenotypes derived from lung compartment biomarkers improve the ability to predict clinical outcomes versus currently accepted phenotypes defined from blood markers alone.

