16.3.7 Aim 3 Statistical Analysis

As with all aims, the final statistical analysis plan will be fixed and filed prior to conducting the analysis. Here, we describe one potential approach for this aim, which will either be confirmed and fleshed out or updated with new methods available at the time of analysis. The primary analysis will include all enrollees to determine if there are latent respiratory phenotypes that are common to all critically ill patients; mechanically ventilated patients enrolled in the APS study will include patients intubated for pneumonia, sepsis, ARDS, and other causes of acute respiratory failure. Secondary analyses will focus within subgroups of patients who have been clinically phenotyped as having sepsis (both pulmonary and non-pulmonary), ARDS, and pneumonia. Some patients will be classified into more than one subgroup.

To approach this aim, a *de novo* latent class analysis (LCA) using previously described methods might be proposed.² For the primary analysis, clinical and respiratory variables along with HME biomarkers measured on the first day of mechanical ventilation would be considered. These variables include protein biomarkers (IL-6, IL-8, TNFR1, MCP1, RAGE, SP-D, Angiopoietin-2, ICAM-1, procollagen peptide-3, protein C, PAI-1 and total protein) along with age, sex, etiology of acute respiratory failure, PaO₂/FiO₂, PEEP, static compliance of the respiratory system, ventilatory ratio,¹⁰ and RALE score.¹¹ Respiratory and HME biomarker data available at a later timepoints for patients who are still intubated may be included in the analysis to determine whether phenotypes identified at the onset of ARF are stable over time and whether new respiratory phenotypes emerge in those who remain in ARF. Once we have determined whether latent respiratory phenotypes are present, we will investigate phenotype generalizability and stability, and test associations between respiratory phenotypes and pre-illness factors such as air pollutant exposure and socioeconomic factors.

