For long-term outcomes, we will focus first on two key hypotheses. First, we hypothesize that acute lung epithelial injury as measured by HME fluid RAGE and SP-D will be associated with development of fibrotic lung changes (increased lung fibrosis scoring on CT, decreased FVC). Second, we hypothesize that the severity of lung endothelial injury as measured by HME fluid Ang-2 and ICAM-1 will be associated with long-term destruction of the lung vascular bed as measured by DLCO. The dependent variables of interest are continuous variables and will be DLCO, FVC, lung fibrosis score. Independent variables include age, sex, HME biomarker data from both day 1 and latest day available, ventilator settings, RALE score, duration of mechanical ventilation, underlying cause of ARF (pneumonia, ARDS, sepsis, other). The initial proposal is for use of linear regression models; dependent variables may be log-transformed to improve fit. Analyses done are expected to include the entire cohort, as well as in subgroups divided by clinical syndrome (pneumonia, ARDS, sepsis). To determine whether long term respiratory outcomes differ by any *de novo* respiratory phenotypes, we can include the phenotype variable and its interaction terms with the main independent variables of interest.

We plan to check for concordance and discordance between novel respiratory phenotypes identified in this Aim and previously derived phenotypes based on clinical and biomarker data and the LCA approach. We will then assess reasons for concordance and discordance. If the same number of clusters are identified with each analysis, standard metrics including Cohen's Kappa will be used to assess the degree of concordance. Identifying a different number of clusters for systemic vs. respiratory phenotypes, or the same number with lack of concordance, may indicate that respiratory phenotypes differ from systemic inflammatory phenotypes. When different numbers of clusters are identified between aims, correlation between cluster variables will be assessed, as well as evaluating whether some clusters function as sub-clusters of those identified in other aims.

Finally, a key question is whether the biologic mechanisms that form the basis for NBBAL endotypes are reflected in the blood. This can be achieved by exploring targeted gene expression profiles and weighted gene cluster network analysis (WGCNA) in bulk RNA seq between peripheral blood PBMCs and NBBAL.

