16.3.9 Aim 3 Expected Output

We anticipate that we will find lung-specific phenotypes, and that sepsis, ARDS and pneumonia will share respiratory phenotypes that will differ from systemic hyper- and hypo-inflammatory phenotypes. In addition, we expect to definitively answer the longstanding question as to how well the biological processes in the airspace can be reflected in the plasma. This study will allow direct comparison between plasma and airspace biomarkers from contemporaneous samples in a large and clinically diverse cohort allowing us to directly address that question.

With regard to long-term outcomes, we anticipate that we will identify key biological signatures in the airspace that will correlate with different long-term outcomes. Specifically, lung epithelial injury biomarkers will correlate with long term restrictive/fibrotic lung dysfunction, and lung endothelial injury markers will correlate with reduced DLCO. It may be that our selected biomarkers do not correlate with these outcomes, in which case we will explore associations with biomarkers of other mechanistic pathways that will be measured for the respiratory LCA.

Lastly, we expect that results from this analysis will shed light on relationships between the alveolar environment and systemic disease. As an example, it has been suggested that COVID-19 pneumonia is driven by self-sustaining inflammatory circuits. However, it is unclear how this mechanism contributes to systemic inflammation and extra-pulmonary organ dysfunction. Similarly, it is unclear how severe pulmonary infections set the stage for impaired systemic immune function. Head-to-head assessment of gene expression pathways and network modules between lung and blood will help address these questions and will define central biologic mechanisms that contribute to disease pathogenesis in the lung versus the periphery.

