16.5.2 Aim 5 Study Objectives

Primary Objective (Aim 5):

We will assess the association between patients' comorbidities, environmental exposures, and biophysical constitution with membership in both previously described and newly identified phenotypes of ARDS, pneumonia, and sepsis. This approach will allow us to identify the contribution of pre-acute illness factors to the pathophysiology of ARDS, pneumonia, and sepsis. There is no intent to develop novel phenotypes under this aim. We will assess the association between exposure history and clinical syndromes, existing molecular phenotypes (e.g., hypo/hyperinflammatory, SRS classes, MARS classes), and phenotypes newly developed under the other aims of this protocol.

The comorbidities of interest are cancer, diabetes mellitus, and cirrhosis; current state and history of these conditions will be considered. The Functional Comorbidity index will also be assessed for contribution to phenotype assignment.

The environmental exposures of interest are cigarette smoking, alcohol use measured using the AUDIT and via blood phosphatidylethanol (PeTH) concentration, air quality index based on 9-digit zip code of residence, and drug use based on urine toxicology screen.

Measures of biophysical constitution are biological sex, age, and body composition (BMI, CT scan imaging), as well as disability assessed using the WHODAS II, cognition assessed using the IQCODE, and frailty assessed using the Clinical Frailty Score.

Exploratory Objectives (Aim 5):

We will assess whether patients' comorbidities, environmental exposures, and biophysical constitution contribute to short-term and long-term outcomes of ARDS, pneumonia, and sepsis, and whether these factors modify the association between phenotype membership and outcomes. Short-term outcomes

include mortality, hospital length of stay, and ICU length of stay. Long-term outcomes include 3-, 6-, and 12-month assessments of physical, respiratory, cognitive, and mental health status.

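### Aim 3's proposed latent class model uses the cause of respiratory failure as a class-defining input, so classes can form or split along ARDS in an analysis meant to find phenotypes common to the syndromes

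*Protocol*

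**What the plan says.** Protocol 16.3.7 presents the LCA as one possible approach, to be confirmed or updated before analysis. It is the only approach worked out for the HME objective. The class-defining variables are 12 HME markers "along with age, sex, etiology of acute respiratory failure", PaO2/FiO2, "PEEP, static compliance of the respiratory system, ventilatory ratio" and RALE score. The primary analysis takes all enrollees together "to determine if there are latent respiratory phenotypes that are common to all critically ill patients". Secondary analyses are planned within sepsis, ARDS and pneumonia.

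The section does not say how etiology is coded for the LCA. Its long-term regression lists the "underlying cause of ARF (pneumonia, ARDS, sepsis, other"). Section 16.3.9 expects that "sepsis, ARDS and pneumonia will share respiratory phenotypes that will differ from systemic hyper- and hypo-inflammatory phenotypes". Section 16.3.7 also says that a different number of clusters, or poor concordance with the systemic classes, may show that respiratory phenotypes are distinct.

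In Aim 5 (16.5.2), "Measures of biophysical constitution are biological sex, age, and body composition". These are to be tested for association with phenotypes that include those newly developed under the other aims.

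**The concern.** An LCA finds classes that explain the association among its inputs. If one input names the syndrome and others shift with that syndrome, the syndrome is itself a ready explanation, and the model can return it as a phenotype. Whether phenotypes cross syndromes should be read from a comparison of classes with syndrome after the classes are formed. It is compromised when the label has helped to form them.

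The respiratory inputs are likely to shift with ARDS. Section 8.1.3 grades "the severity of ARDS based the level of hypoxemia (P:F and S:F ratios") and requires bilateral infiltrates, which RALE also reflects.

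Two later steps inherit the problem. Classes that mirror ARDS would probably disagree with the hyper- and hypo-inflammatory classes, and 16.3.7 could read that as a distinct respiratory phenotype. The long-term regression includes both phenotype and cause, which would be nearly collinear. Separately, an Aim 5 association of age or sex with an Aim 3 phenotype is partly built in, because both are LCA inputs.

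Other parts of the protocol keep such variables outside the class model. Aim 1 (16.1.5) fits classes first and then tests for variation by syndrome. Aim 4 (16.4.7.1) leaves severity scores and outcomes out.

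**Working it through.** The plan gives no figure to reproduce, so the check asks when the listed inputs would yield a class equal to ARDS.

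**From the documents.** 1,500 ventilated patients, 600 with ARDS (16.3.8), so 600/1500 = 0.40. Inputs: 12 HME markers, 5 respiratory variables, age, sex, etiology (16.3.7).

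**Assumed.** ARDS shifts each respiratory input by *d* SD; etiology is one four-level label with ARDS as a level; inputs are independent within class; BIC chooses the number of classes.

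**Step 1: why the label matters.** Compare one class with two classes equal to ARDS and not ARDS, with no protein structure.
- Label: the gain in log-likelihood per patient is −0.4 ln 0.4 − 0.6 ln 0.6 = 0.673. The mixing proportions cost the same 0.673. The net is zero, so the label alone creates no class, but it makes membership known.
- Respiratory inputs: pooled variance is 1 + 0.4 × 0.6 × d² = 1 + 0.24d². The gain in twice the log-likelihood is 1500 × 5 × ln(1 + 0.24d²).
- BIC cost of the second class: 1 mixing parameter + 2 × 18 means and variances + 1 for sex + 3 for etiology = 41; 41 × ln 1500 = 41 × 7.313 = 299.8.
- At d = 0.5: 7500 × ln 1.06 = 437.0, which exceeds 299.8, so the ARDS split is accepted.
- Break-even: ln(1 + 0.24d²) = 299.8/7500 = 0.0400, so d is about 0.41.

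**Step 2: simulation, no airspace structure** (EM, 1 to 4 classes by BIC, 3 to 4 runs per cell; ARI is the adjusted Rand index with ARDS).

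| ARDS shift | All listed inputs | Etiology removed | Proteins, age, sex |
|---|---|---|---|
| 0 SD | 1 class | 1 class | 1 class |
| 0.5 SD | 2 classes, ARI 0.99 | 1 class | 1 class |
| 0.8 SD | 2 classes, ARI 1.00 | 2 classes in 2 of 3 runs, mean ARI 0.29 | 1 class |
| 1.0 SD | 2 classes, ARI 1.00 | 2 classes, ARI 0.56 | 1 class |

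A repeat at 0.5 to 0.8 SD gave ARI 0.96 to 1.00 with all inputs. Without etiology it gave one class at 0.5 SD and ARI 0.34 to 0.40 at 0.8 SD.

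**Step 3: a real airspace class, independent of ARDS** (30% of patients, 8 of 12 proteins shifted 1.0 SD). Cells show number of classes, then ARI with ARDS / with the airspace class.

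| ARDS shift | All listed inputs | Etiology removed | Proteins, age, sex |
|---|---|---|---|
| 0.5 SD | 3; 0.52 / 0.37 | 2; 0.00 / 0.72 | 2; 0.00 / 0.72 |
| 0.8 SD | 3 to 4; 0.58 / 0.33 | 2; 0.00 / 0.72 | 2; 0.00 / 0.72 |
| 1.0 SD | 4; 0.58 / 0.34 | 3; 0.31 / 0.37 | 2; 0.00 / 0.72 |

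The lower airspace ARI with all inputs mostly reflects extra splitting. In runs with a protein shift of about 0.7 SD, assigning each full-input class to its majority airspace class recovered that class in about 85 to 89% of patients in most runs. With a 0.7 SD class, dropping etiology restored the correct two classes at ARDS shifts of 0.5 to 0.8 SD. With a protein shift of only 0.5 SD, the full inputs returned ARDS alone (ARI 0.99), but the protein model also found only one class.

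**The case against.** **The text is provisional.** The LCA is something that might be proposed. That lowers the urgency. The input list is still the default that the final plan starts from.

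**A reader might infer that the plan cannot show shared phenotypes.** The documents do not support that. The label pushes classes apart by syndrome, so sharing found despite it would still count. The ARDS subgroup analysis holds ARDS status constant, and the primary objective based on NBBAL RNA sequencing lists no etiology input. The rescue is only partial in the pneumonia subgroup. At n = 600 with an assumed 30% ARDS, the full inputs again reproduced ARDS (ARI 0.99 to 1.00) at shifts of 0.8 to 1.0 SD, though not at 0.5 SD.

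**A reader might infer that a real airspace class would be hidden.** If two classes are forced and severity shifts are 1.0 to 1.5 SD, agreement with the airspace class falls to 51%, which is chance. The plan does not force two classes, and the protocol's explicit LCA procedure (16.4.7.1) fits 1 to 5 and selects by fit.

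**The respiratory variables look like the same fault.** They are part of primary objective 2 (16.3.2), so demoting them would change the question.

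**Secondary objective 3 looks unprotected.** It is to "Determine whether phenotypes derived from lung compartment biomarkers improve the ability to predict clinical outcomes versus currently accepted phenotypes defined from blood markers alone", while the classes also contain age and ventilator physiology. Section 12.2.4 already suggests adding the variables used to derive clusters, and the 16.3.7 long-term regression already includes age, sex, ventilator settings, RALE and cause. Much of that request is covered.

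**The simulation is stylised.** Syndromes overlap (1050 + 600 + 600 = 2250 memberships in 1,500 patients), whereas one exclusive label was simulated. The HME safety screen in 16.3.5 may narrow the severity range. Both points limit the size of the effect but leave the mechanism in place.

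**Conclusion.** The point holds for etiology. With the listed inputs, the label can create or split classes along ARDS even when the proteins carry no class structure, once ARDS patients differ by about 0.5 SD or more on the respiratory inputs. The break-even is near 0.41 SD under the assumptions above, and there is no effect at 0 SD. The resulting discordance with systemic classes could then be misread under 16.3.7. When an airspace class is strong enough for the proteins to show it, it is still found, but divided by ARDS.

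This rests on ARDS being a level of etiology in the LCA, which is inferred from the regression list in the same section, and on a shift size that the documents do not give. The simulations show the mechanism and do not forecast the study's result. The Aim 5 point follows from the input list alone and was not quantified.

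**What to change.** In 16.3.7, remove etiology from the LCA inputs and cross-tabulate the final classes against syndrome as an external variable. Keep the clinical respiratory variables. Add an LCA on HME proteins alone as a required sensitivity analysis, and report the agreement of classes with ARDS status in both models. The second model is needed because respiratory variables can still recover ARDS in part at larger shifts (ARI 0.56 at 1.0 SD without etiology).

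In 16.5.2, state that age and sex associations will not be interpreted for any phenotype that used them as inputs.

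The cost is analysis-plan wording and one extra model fit, with no new data. Class separation will be somewhat weaker in the protein-only model, mainly in the subgroups of 600, where it often missed a 0.7 SD airspace class.

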12.2.4 Validation

When patterns or structures are discovered through data analysis, these identified patterns should be validated in the sense of demonstrating sturdiness to small changes in the dataset used to find the structures. Predictive and estimation instruments should also be validated. Split-sample validation (validating on a holdout sample) is often used and may be appropriate in some instances. Repeating the process of splitting into derivation and validation samples a few times can reveal volatility of the split-sample approach when the sample is of insufficient size, and splitting the sample reduces the derivation sample size. When the statistical approach allows, cross-validation and bootstrap validation should be considered in order to maximize use of information and to optimize the reliability of the validation. Carefully repeating, inside each resampling loop, all learning/data analysis steps can reduce overfitting.

Validation analyses should include an assessment of the stability of discovered patterns, feature selection, etc. In high-dimensional situations in which “winning” features are sought, it is important to validate the ability of the data to find such “winners.” This can be done by, for example, computing bootstrap confidence intervals for importance rankings of competing features.^{21,22} Human supervision of feature selection may be important and adopted in specific cases depending on individual project goals. When the goal is to make absolute predictions (outcome risks, life expectancy, etc.), validations should include information on the absolute predictive accuracy (e.g., overfitting-corrected smooth calibration curves).

When patient clustering or any method that categorizes patients is used, additional validation should be considered. For example, when the goal is to predict patient outcome or to estimate differential treatment effect, an approach to validating patient clustering might be:

- Start with cluster indicator variables as the only variables (other than background covariates that may be included in all models) in the model predicting patient outcome, or as main effect and interaction-with-treatment effects in an analysis of treatment effect heterogeneity. Measure the predictive information in the categorical cluster indicators.

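### For phenotypes built from HME and clinical variables, the Aim 3 model tests what the phenotype adds to its own components, not whether 12-month lung outcomes differ by phenotype

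*Protocol*

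**What the plan says.** Both primary objectives of Aim 3 (16.3.2) are to find acute phenotypes and "identify their association with short-term and long-term clinical outcomes". The second of them builds the phenotypes from HME proteins on day 1 of ventilation together with clinical respiratory variables.

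Section 16.3.7 suggests a latent class analysis (LCA) for this. Its inputs are twelve HME proteins from the first day of ventilation, age, sex, etiology of respiratory failure, PaO2/FiO2, PEEP, static compliance, ventilatory ratio and RALE score.

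For DLCO, FVC and fibrosis score, the same section proposes linear regression: "Independent variables include age, sex, HME biomarker data from both day 1 and latest day available, ventilator settings, RALE score, duration of mechanical ventilation", followed by cause of respiratory failure in four categories. It then turns to the phenotypes. The purpose is given as "To determine whether long term respiratory outcomes differ by any" de novo phenotype, and the method is that "we can include the phenotype variable and its interaction terms with the main independent variables of interest".

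Section 16.3.8 gives the power: with 200 ventilated patients, a 10-df base model and 4 added df, Cohen's f² is 0.08 at 90% power and 5% type I error. It describes the target as improved model fit from adding the phenotypes and their interactions.

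Section 12.2.4 offers a staged way to validate clusters: "Start with cluster indicator variables as the only variables (other than background covariates that may be included in all models) in the model" for the outcome. The variables that derived the clusters enter only at the third stage.

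**The concern.** The stated question is a comparison between groups: do patients in different phenotypes have different lung function and fibrosis at 12 months? The proposed model answers another question: given a patient's HME biomarkers, RALE score, ventilator settings and so on, does the class label tell us anything more? The label is computed from largely the same variables, so the two answers can be opposite.

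The section's own hypotheses make this likely. It expects HME RAGE and SP-D to track fibrotic change, and HME Ang-2 and ICAM-1 to track DLCO. If that is right, phenotypes that differ on those markers will differ in outcome through those markers, and adjusting for the markers removes the difference.

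Latest-day biomarkers and duration of ventilation add to the problem. Both are observed after the first-day phenotype and may lie on its path to the outcome.

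At stake is the long-term part of a primary objective. Section 16.3.7 gives no other model relating these phenotypes to DLCO, FVC or fibrosis score.

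**Working it through.** **1. Overlap of the two lists (16.3.7).**

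| LCA input | Covariate in the outcome model? |
|---|---|
| Twelve first-day HME proteins | Yes, as HME biomarker data from day 1 (and latest day); number of markers not stated |
| Age, sex | Yes |
| Etiology of respiratory failure | Yes, as underlying cause |
| RALE score | Yes |
| PEEP | Yes, if counted among ventilator settings |
| PaO2/FiO2, compliance, ventilatory ratio | Not named |

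Latest-day biomarkers and duration of ventilation are covariates but not inputs.

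**2. The plan's own power figure.** The partial F test has u = 4 and v = 200 − 10 − 4 − 1 = 185. With noncentrality λ = f²·N = 0.08 × 200 = 16, power is 90.4%, and the f² giving 90% is 0.079. With λ = f²·(u + v + 1) = 0.08 × 190 = 15.2, power is 88.7% and the f² is 0.083. The stated 0.08 is reproduced.

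**3. What that f² measures.** f² = (R²_full − R²_base) / (1 − R²_full). It is the gain from phenotype given the base model, not the difference between phenotypes. Suppose the class is assigned from the day-1 inputs, and the outcome is linear in markers already in the base model plus independent error. Then R²_full = R²_base in the population and f² = 0, however far apart the phenotype means are.

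**4. Size, by simulation.** The documents give no class separation, prevalence or R² for this, so all of these are assumptions:
- twelve normal markers and three classes (40%, 35%, 25%);
- the middle class shifted on six markers and the top class on all twelve, by 1 or 2 within-class SD;
- classes recovered by a Gaussian mixture in 400 patients, of whom 200 are analysed;
- outcome R² of 0.08 or 0.15, with the signal carried either by the mean of four markers or by the latent class itself;
- 150 runs per row, so Monte Carlo error is up to √(0.25/150), about 4 points.

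Percentage of runs with p < 0.05:

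| Signal carried by | R² | Shift (SD) | Phenotype alone | Phenotype given 4 markers | Phenotype given 12 markers, two days | Phenotype + interactions given 4 markers |
|---|---|---|---|---|---|---|
| Markers | 0.08 | 1 | 77 | 5 | 5 | 4 |
| Markers | 0.08 | 2 | 91 | 3 | 2 | 3 |
| Markers | 0.15 | 1 | 98 | 5 | 5 | 7 |
| Markers | 0.15 | 2 | 99 | 4 | 7 | 3 |
| Class | 0.08 | 1 | 81 | 48 | 13 | 39 |
| Class | 0.08 | 2 | 95 | 49 | 15 | 35 |
| Class | 0.15 | 1 | 99 | 81 | 30 | 63 |
| Class | 0.15 | 2 | 100 | 86 | 31 | 67 |

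When the markers carry the signal, the adjusted tests reject at about the 5% null rate, as step 3 predicts. When the class carries it, power falls but does not vanish.

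**5. Fit with the 10-df base model.** Age 1, sex 1, ventilator settings at least 1, RALE 1, duration 1 and cause 3 make 8 df. Two markers on two days bring this to 12; all twelve on two days bring it to 32. The twelve-marker column is therefore a larger model than the one powered and shows an extreme.

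**The case against.** The strongest reply is that 16.3.7 fixes nothing. It calls its text one potential approach and its regression an initial proposal, and it says the phenotype can be included. The final model belongs to a statistical analysis plan that is not shown. Section 12.2.4 already describes the indicator-first stage, and 16.3.8 openly frames its power as a gain in fit. All of this stands and limits the weight of the point. It does not remove it: 16.3.7 attaches a specific method to a specific question, the method does not answer that question, and 16.3.8 rests adequacy of sample size on it.

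A reader might infer several stronger things that the documents do not support:

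- **That true differences are bound to be reported as absent.** They are not. In the simulations 13–86% power remains when the class itself drives outcome. No passage says how a null phenotype term would be interpreted.
- **That Aim 3 breaks a rule in 12.2.4.** The staged order there is advice, offered as an approach that might be used.
- **That the f² of 0.08 is wrong.** It reproduces; it simply concerns incremental value.
- **That all Aim 3 phenotypes are affected.** Those derived from RNA sequencing of NBBAL cells (primary objective 1) do not share these inputs.
- **That phenotype-by-marker interactions are invalid.** The protocol does not say which variables are interacted; its worked example uses a two-level categorical variable. Coding of a continuous marker changes the meaning of the phenotype main effect but not the joint F test.

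It is also fair that the near-5% results follow from generating the outcome from the very markers then adjusted for. That scenario is, however, the one 16.3.7 hypothesises.

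**Conclusion.** The point holds for phenotypes built from HME and clinical variables. As proposed, the model estimates the value of the phenotype beyond its own components, while 16.3.7 says it shows whether outcomes differ by phenotype. Real differences can be hidden, and under the section's marker hypotheses they usually would be.

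That the question and the model do not match follows from the text alone. The size does not: it depends on assumed class separation, prevalence, R² and the number of markers adjusted for. The direction was the same in every setting tried.

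The incremental question is legitimate in itself, but it is not what the objective asks. Even secondary objective 3 in 16.3.2 compares lung phenotypes with blood-based phenotypes, not with their own HME inputs. Because the text is provisional, this is a correction to make before the analysis plan is fixed, not a flaw in the study design.

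**What to change.** In 16.3.7:

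1. For each 12-month outcome, first estimate the difference between phenotypes with phenotype plus background or pre-illness covariates only, following the staged order of 12.2.4. Class probabilities are preferable to hard assignment, since 12.2.5 asks that uncertainty in membership be carried forward. Age and sex are also LCA inputs; if they are kept as background covariates, say that the comparison is at given age and sex. Leave latest-day biomarkers and duration of ventilation out of this model.
2. Then report a separate second model that adds the LCA inputs and any phenotype-by-marker interactions, labelled as incremental value beyond the components.

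In 16.3.8, state that f² = 0.08 refers to the second model.

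The cost is one extra model per outcome and a few lines of text. No new data are needed.
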